## 5.0 PATIENT EVALUATION

### 5.1 Pretreatment Evaluation. (To be completed within 14 days of study entry unless otherwise indicated)

- a. History and physical examination, including vital signs, height, weight and performance status.
- b. Bone marrow aspirate and/or biopsy within 28 days of treatment start. Cytogenetics, flow cytometry and molecular studies may be performed as clinically indicated.
- c. CBC with differential (within 7 days).
- d. Serum chemistry: BUN, creatinine, bilirubin, AST and/or ALT, magnesium, glucose, uric acid (within 7 days).
- e. Have a negative serum or urine pregnancy test within 10 to 14 days of enrolling

(A second pregnancy test will be performed within 24hrs of starting therapy and both negative pregnancy tests will be required for starting therapy.)

- f. Peripheral blood for baseline correlative immune studies (if patient agrees to correlatives).
- g. Signed informed consent.

## 5.2 During treatment Evaluation.

- a. Physical examination (including vital signs, weight, performance status) every 28 days ( $\pm 7$  days) for the first 3 months, then every 3 months until 12 months from the start of therapy; then every 6 months ( $\pm 2$  months).
- b. CBC with differential (differential not required if  $WBC \leq 0.5 \times 10^9/L$ ), at least once weekly for the 1st cycle, then every 2 to 4 weeks during cycles 2-6, and then every 4 weeks ( $\pm 14$  days) thereafter as long as they are on study.
- c. Serum chemistry profile at least once weekly for the 1st cycle, then every 2 to 4 weeks during cycles 2-6, and then at least every 4 weeks ( $\pm 14$  days) during active treatment.
- d. Bone marrow aspiration and/or biopsy after cycle 1, after 3 months of therapy ( $\pm 2$  weeks), then every 3 months ( $\pm 1$  month) until month 12, then every 6 months ( $\pm 2$  months). No repeat bone marrow is necessary if non-response or progressive disease can be unequivocally diagnosed from peripheral blood tests or, in patients with a  $WBC < 0.4 \times 10^9/L$ , if the bone marrow is considered non-contributory by the investigator at any point.
- e. Flow cytometry for MRD after cycle 1, after 3 months of therapy ( $\pm 2$  weeks), then every 3 months ( $\pm 1$  month) until month 12, then every 6 months ( $\pm 2$  months).
- f. Peripheral blood for correlative immune studies once weekly for the 1st cycle, and once at the end of cycle 3, 6, and 12. (if patient agrees to correlatives)
- g. Patients will be followed for survival every 6 to 12 months after completion of active treatment and while still on study or be enrolled on the leukemia department long-term follow-up umbrella protocol.
- h. Women of child bearing potential must have a negative pregnancy test prior to each cycle of therapy.

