### 4.3 Duration of Therapy

In the absence of treatment delays due to adverse events, the treatment will be administered continuously for a total of 24 months. The patient will continue on the study unless one of the following criteria applies:

- Clinically significant progressive disease as defined by Modified International Working Group Criteria (**see section 9**).
- Undergoing allogeneic bone marrow transplant.
- Intercurrent illness that prevents further administration of treatment.
- Patient request.
- Unacceptable toxicity.
- Need for alternative treatment.
- General or specific changes in the patient's condition that render the patient unacceptable for further treatment in the judgment of the investigator or treating physician.

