**Infection**

If a patient develops a clinically significant infection of any grade, treatment may be delayed or withheld until the infection is clinically controlled (e.g., the patient is afebrile and with improving signs/symptoms). Treatment may then resume at the same dose.

Description of Event: Non-Hematologic	Dose Modifications
Drug-related clinically significant non-hematologic Grade 3-4 adverse event. 	Hold therapy until recovery to Grade $\leq$ 1, then re-start and reduce dose by one dose level. If toxicity recurs, hold therapy until recovery to grade $\leq$ 1, then re-start and reduce one dose level. Dose reductions below dose level -2 will be not be considered. If dose level -2 is considered intolerable, the patient will should be taken off study.
Persistent grade 2 toxicity considered clinically significant or unacceptable. 	Consider holding therapy until recovery to Grade $\leq$ 1, then re-start and reduce one dose level. If toxicity recurs, hold therapy until recovery to grade $\leq$ 1, then re-start and reduce one dose level. Dose reductions below dose level -2 will be not be considered. If dose level -2 is considered intolerable, the patient will should be taken off study.
Any occurrence of <math>\geq</math> drug related Grade 2 neurologic events	The patient's study drug doses are to be re-evaluated in consultation with the Principal Investigator, and may be reduced according to the above parameters, or discontinued based on the event, and the time to resolution to $\leq$ Grade 1.

 Includes, but is not limited to, bacteremia, systemic fungal infections, cytomegalovirus (CMV) infection, *Pneumocystis carinii* pneumonia (PCP), disseminated *Varicella*, etc.

 Excludes NCI CTC  $\geq$  grade 2 drug-related neurologic toxicities, grade 2 alopecia, and grade 3 anorexia, transient elevations in hepatic transaminases or alkaline phosphatase based on institutional normals without clinical significance, and nausea/vomiting, diarrhea or mucositis that resolves (with or without supportive care) to < grade 2 within 48 hours of onset to grade 3.

 Excludes NCI CTC grade 4 transient elevations in hepatic transaminases or alkaline phosphatase based on institutional normals without clinical significance.

Therapy will be continuous; interruptions and dose-adjustments for toxicity will be implemented as needed, based on above table.

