## 8.0 STATISTICAL CONSIDERATIONS

### STATISTICAL CONSIDERATIONS

This is a phase II study of lenalidomide as a maintenance therapy in patients with high risk AML and in first or second remission. The primary objective is to assess whether the maintenance therapy can improve relapse-free survival (RFS), which is defined as the time interval from date of treatment start until the date of death or disease relapse. Patients who are alive and relapse-free at the last follow-up date will be censored at that time.

The study will be continuously monitored for the primary endpoint, RFS, using the method of Thall, Wooten, and Tannir (2005). Our goal is to improve the median RFS from 8 months (based on historical treatment) to 10.5 months using lenalidomide maintenance therapy. It is assumed that the RFS time is exponentially distributed with a median of  $\lambda_E$  among patients who receive lenalidomide as a maintenance therapy, and a median of  $\lambda_H$  is assumed for the historical treatment. Further, we assume that  $\lambda_H$  follows an inverse gamma distribution, i.e.,  $\lambda_H \sim \text{IG}(3.6, 20.8)$ , which has a mean of 8 months and variance of 40. To reflect the little prior knowledge of  $\lambda_E$  we assume an inverse gamma prior distribution with the same mean of 8 months and a much larger variance of 500, i.e.,  $\lambda_E \sim \text{IG}(2.128, 9.024)$ . The trial will be stopped early if  $\text{Pr}(\lambda_E > \lambda_H + \delta | \text{data}) < pL$ , where  $\delta = 2.5$  months and  $pL=0.05$  and this futility monitoring rule will be first applied when 10 patients have been enrolled. A maximum of 50 patients will be enrolled into this study at an expected accrual rate of 1 patient per month. From historical experience, 25% of patients in this cohort may become eligible for stem cell transplant and may come off study. For purposes of this analysis, these patients will be censored at the time of receiving transplant. Patients will be followed up for an additional 12 months after all patients have been enrolled. The trial will be conducted using the Clinical Trial Conduct (CTC) website maintained by the Department of Biostatistics at MDACC.

The operating characteristics of the design, based on an overall assumed accrual rate of 2 patients per month with 5000 simulated trials per scenario, are given in the following table. One-Arm Time-to-Event Simulator (version3.0.1) was used for the design and simulation.

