### **9.1.6 Confirmed Relapse**

Recurrence of disease as noted by: > 30% peripheral blasts, or > 20% bone marrow blasts. If the bone marrow blasts are between 6% and 20%, 2 serial bone marrow examinations at least 2 weeks apart demonstrating successive increase in blasts by at least 2% will also be a confirmed relapse.

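### The plan does not require relapse status or date to be collected after lenalidomide stops early, and Section 8 does not tie RFS censoring to the last disease assessment

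*Combined protocol and SAP*

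**What the plan says.** Section 8.0 of the combined protocol and SAP makes RFS the primary endpoint, "which is defined as the time interval from date of treatment start until the date of death or disease relapse". Its censoring rule is "Patients who are alive and relapse-free at the last follow-up date will be censored at that time". The only other censoring event it names is transplant, expected in 25% of patients.

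Section 9.1.6 defines confirmed relapse by "> 30% peripheral blasts, or > 20% bone marrow blasts", or, for marrow blasts of 6% to 20%, by two serial marrows with rising blasts.

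Marrow (5.2d) and MRD flow (5.2e) are listed under "5.2 During treatment Evaluation". Item 5.2b continues the CBC for as long as the patient is on study, whereas 5.2c limits chemistry to active treatment. Item 5.2g covers the later period: "Patients will be followed for survival every 6 to 12 months after completion of active treatment" while still on study, "or be enrolled on the leukemia department long-term follow-up umbrella protocol".

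Section 4.3 lists the reasons for which a patient does not continue on study. They include "Unacceptable toxicity", patient request, intercurrent illness and need for alternative treatment. Table 2 adds "If dose level -2 is considered intolerable, the patient will should be taken off study".

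Section 8.0 also plans 12 further months of follow-up after the last enrolment, without saying what is assessed.

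**The concern.** A patient who stops lenalidomide in remission, without transplant, is still at risk for the primary endpoint. The endpoint definitions support this: Section 9.1.8 counts withdrawal for an adverse event as an event-free survival event, but neither definition of RFS (8.0 or 9.1.7) counts it, and no text censors RFS at the stop. The scheduled data that could show a relapse, however, are tied to treatment or to being on study.

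If such a patient is then contacted only for survival, a relapse is recorded at a later contact, at death, or not at all. Each of these lengthens RFS, which is the direction of the trial's aim. The same data feed the futility rule, so an ineffective treatment would be stopped less often. The posterior probability that forms the primary analysis would also rise.

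**Working it through.** **Inputs from Section 8.0.** Historical median 8 months, target 10.5 (δ = 2.5). Priors λ_H ~ IG(3.6, 20.8) and λ_E ~ IG(2.128, 9.024). Stop if Pr(λ_E > λ_H + 2.5 | data) < 0.05, from 10 patients. Maximum 50 patients; accrual 1 per month in the text and 2 per month in the simulations; 12 months of further follow-up; 25% transplanted and censored.

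**Assumptions not in the documents.** Share stopping before relapse for non-transplant reasons, 10% to 40%. Median survival after relapse, 3 to 9 months.

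**Step 1. Reproduce the plan's table.** With exponential RFS the update is λ_E | data ~ IG(2.128 + events, 9.024 + ln2 × total time). The rule was checked at each arrival, with 2 patients per month at fixed spacing and 3,000 simulated trials per scenario.

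| True median (months) | 4 | 6 | 8 | 10.5 | 12 |
|---|---|---|---|---|---|
| Plan, Pr(stopped early) | 0.968 | 0.410 | 0.102 | 0.030 | 0.017 |
| Reproduced | 0.977 | 0.429 | 0.116 | 0.039 | 0.023 |

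All five agree within 2 percentage points. With Poisson arrivals the value at median 8 is 0.122, just outside that margin.

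**Step 2. Hand calculation.** The exponential estimate of the median is ln2 × person-time / events. Suppose a share p stops before relapse and only death is then seen, with post-relapse median survival m. Mean recorded time rises by p × m/ln2. With no censoring, the estimate is therefore 8 + p × m:

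- p = 0.2, m = 3: 8 + 0.6 = 8.6 months
- p = 0.2, m = 6: 8 + 1.2 = 9.2 months
- p = 0.2, m = 9: 8 + 1.8 = 9.8 months

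Administrative censoring, uniform over 12 to 62 months, reduces these to 8.6, 9.1 and 9.6.

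**Step 3. Simulation with the plan's features.** Accrual 1 per month, 25% transplant censoring, 24-month treatment cap, true median 8, 2,500 trials per cell. Estimated median RFS in months:

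| Share stopping early | Relapse fully recorded | Dated at next 6- / 12-month contact | Dated at death, m = 3 / 6 / 9 |
|---|---|---|---|
| 10% | 7.9 | 8.3 / 8.4 | 8.3 / 8.6 / 8.8 |
| 20% | 8.0 | 8.4 / 8.7 | 8.6 / 9.05 / 9.5 |
| 30% | 8.0 | 8.6 / 9.0 | 8.9 / 9.6 / 10.2 |
| 40% | 8.0 | 8.7 / 9.4 | 9.2 / 10.25 / 11.1 |

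The 24-month cap alone, with no early stopping and m = 6, moves the estimate from 7.97 to 8.22.

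**Step 4. Effect on the decision quantities.**
- With 20% stopping and true median 8, mean Pr(λ_E > λ_H + 2.5 | data) rises from 0.38 to 0.43–0.53. Futility stopping falls from about 0.12 to 0.08–0.09.
- With true median 6, futility stopping falls from 0.41 to about 0.28 (20% stopping) or 0.20–0.22 (30% stopping).

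**Step 5. The other reading of the censoring rule.** If RFS is censored when treatment stops and stopping is unrelated to relapse risk, the estimate stays at 7.95 to 8.04 months. At 20% stopping, mean events fall from 35.7 to 29.9. If patients who stop then relapse 1.5 times faster, this censoring gives 7.94 months against 7.49 with relapse fully recorded.

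**The case against.** The strongest reply is that the plan does not limit follow-up to survival. A reader might infer from 5.2g that only survival is followed, and the text does not support that. The item offers the umbrella protocol as an alternative, which may or may not record relapse. The CBC continues while on study, and peripheral blasts alone can establish relapse. The heading over the marrow schedule is not decisive, since 5.2g sits under the same heading. The further 12 months of follow-up are not limited to survival either.

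The censoring rule also asks for patients who are both alive and relapse-free, and a survival contact does not establish the second. If patients who stop leave the study, the last follow-up date may be the off-study date. Step 5 then shows no upward bias when stopping is non-informative.

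These points make the bias conditional. They do not close the gap. Section 4.3 and Table 2 describe toxicity and other reasons as ending study participation, so the continuing CBC does not clearly reach these patients. Where it does, blood confirms relapse only above 30% blasts; the other routes need marrow. Nothing states that the umbrella protocol supplies relapse dates, and Section 8.0 does not say which date is used for censoring.

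The size is also fairly challenged. Steps 2 and 3 assume that no relapse after stopping is recorded on time. If half are (an assumption), 20% stopping gives about 8.3 to 8.8 months.

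**Conclusion.** The gap stands: the primary endpoint needs relapse dates that the plan does not require once lenalidomide stops without relapse, death or transplant, and the censoring date is left open. An upward bias follows if the last follow-up date is taken to be a survival contact. With a true median of 8 months, 20% stopping early and post-relapse median survival of 3 to 9 months, the estimate is about 8.4 to 9.6 months, a shift of 0.4 to 1.6 months against a 2.5-month target. The stopping share and post-relapse survival are assumptions, so this is a range and not a prediction.

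Three stronger inferences should not be drawn.
- That RFS is biased upward whatever the reading: Step 5 shows otherwise.
- That an inactive drug would reach the 10.5-month target. With 30% stopping, 9-month post-relapse survival and no relapse captured, the simulation gives 10.2 months; 10.5 appears only when transplant censoring is also left out. That stacks unfavourable assumptions.
- That toxicity is the main reason for stopping: the documents give no discontinuation figures.

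**What to change.** In Section 5.2g, state that for every patient who stops lenalidomide without relapse, death or transplant, relapse status and date are collected until relapse, death, transplant or study end. The sources are existing clinic counts, marrow reports, outside records or the umbrella protocol. Name an interval close to the on-treatment schedule, and say whether the umbrella protocol supplies relapse dates. Reconcile this with Section 4.3 and Table 2, so that it is clear whether a patient who stops treatment remains in follow-up for RFS.

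In Section 8.0, state that stopping lenalidomide is not itself a censoring event for RFS. State also that patients without an event are censored at the last date documented relapse-free, not at the last survival contact.

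This is a cheap improvement: a few record checks and CRF fields per off-treatment patient, with no added marrow or visit. One limit remains: relapses at 6% to 20% marrow blasts may still be dated late where no clinical marrow is done.

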## 6.0 DOSING DELAYS / DOSE MODIFICATIONS FOR SUBSEQUENT CYCLES

### 6.1 Dose levels for dose adjustments Table 1

Dose Level	Lenalidomide Dosing
-2	5 mg PO Every other Day
-1	5 mg PO Daily
0 (Starting dose level)	10 mg PO Daily
1	15 mg PO Daily
2	20 mg PO Daily

6.1.1. Dose levels different than dose described may be allowed after discussion with the PI.

**Table 2. Non-Hematologic Toxicity**

**Drug-related Grade 2 Toxicity**

Initiation/continuation of treatment will be delayed if a > Grade 1 drug-related clinically significant non-hematologic toxicity has occurred or worsened and not yet returned to < Grade 2 prior to the start of the next dose.

**Infection**

If a patient develops a clinically significant infection of any grade, treatment may be delayed or withheld until the infection is clinically controlled (e.g., the patient is afebrile and with improving signs/symptoms). Treatment may then resume at the same dose.

Description of Event: Non-Hematologic	Dose Modifications
Drug-related clinically significant non-hematologic Grade 3-4 adverse event. 	Hold therapy until recovery to Grade $\leq$ 1, then re-start and reduce dose by one dose level. If toxicity recurs, hold therapy until recovery to grade $\leq$ 1, then re-start and reduce one dose level. Dose reductions below dose level -2 will be not be considered. If dose level -2 is considered intolerable, the patient will should be taken off study.
Persistent grade 2 toxicity considered clinically significant or unacceptable. 	Consider holding therapy until recovery to Grade $\leq$ 1, then re-start and reduce one dose level. If toxicity recurs, hold therapy until recovery to grade $\leq$ 1, then re-start and reduce one dose level. Dose reductions below dose level -2 will be not be considered. If dose level -2 is considered intolerable, the patient will should be taken off study.
Any occurrence of <math>\geq</math> drug related Grade 2 neurologic events	The patient's study drug doses are to be re-evaluated in consultation with the Principal Investigator, and may be reduced according to the above parameters, or discontinued based on the event, and the time to resolution to $\leq$ Grade 1.

 Includes, but is not limited to, bacteremia, systemic fungal infections, cytomegalovirus (CMV) infection, *Pneumocystis carinii* pneumonia (PCP), disseminated *Varicella*, etc.

 Excludes NCI CTC  $\geq$  grade 2 drug-related neurologic toxicities, grade 2 alopecia, and grade 3 anorexia, transient elevations in hepatic transaminases or alkaline phosphatase based on institutional normals without clinical significance, and nausea/vomiting, diarrhea or mucositis that resolves (with or without supportive care) to < grade 2 within 48 hours of onset to grade 3.

 Excludes NCI CTC grade 4 transient elevations in hepatic transaminases or alkaline phosphatase based on institutional normals without clinical significance.

Therapy will be continuous; interruptions and dose-adjustments for toxicity will be implemented as needed, based on above table.

**6.2 Myelosuppression:** Patients with leukemias and MDS usually present with abnormal peripheral blood counts at the time therapy is started and some myelosuppression is an expected event during the course of therapy for acute leukemias and myelodysplastic syndromes. Thus, dose-adjustments or treatment interruptions for myelosuppression will be planned only for confirmed, severe neutropenia or

thrombocytopenia that is confirmed for at least 1 week according to the following guidelines:

6.2.1.1 Patients in remission who have sustained low counts (for at least 7 days) of neutrophils  $<0.5 \times 10^9/L$  or a platelet count  $<20 \times 10^9/L$  should have therapy held until resolution. The patient may then receive subsequent treatment at 1 dose level reduction. A reduction of 2 dose levels may be considered if the myelosuppression was deemed severe and/or life threatening by the treating physician, and if it is in the patient's best interest.

## **7.0 AGENT FORMULATION AND PROCUREMENT**

Lenalidomide will be supplied by Celgene as part of this investigational study. Commercial drug supply will be used.

### **7.5 CORRELATIVE STUDIES**

Collection of Immune Modulation Studies will be requested from all patients on study. Heparanized blood specimens will be collected for assays to assess correlates of immune system activity prior to beginning treatment, at day 7, 14, 21, and 28 of Cycle 1 ( $\pm$  3 days), and at the end of Cycle 3, 6 and 12 ( $\pm$  14 days). The assays include:

1. Enumeration of immune cells (by multi-parameter flow cytometry)
2. Quantification of cytokines/chemokines (by Luminex® Multiplex assay)
3. NK cell functional assay (by Calcein-release direct cytotoxicity)
4. KIR genotyping (by SSP- or SSO-PCR analysis)
5. NK cell gene expression profile (using custom NK cell codeset on the nanoString platform)

These assays will be used to identify biological correlates of lenalidomide immune-modulatory activity, and to correlate immune function, genotype, and immunomodulation with disease response or relapse.

Sample requirements:

10 mL of blood drawn into a sodium heparin (green top) tube.

Sample preparation/handling:

Keep samples at room temperature. Notify the [name] Lab by email for same-day sample pickup. Use pager or phone as backup contact:

[name]

e-mail: [[contact]](mailto:[contact])

[contact]

[contact]

[name]  
 e-mail: [[contact]](mailto:[contact])  
 [contact]

## 8.0 STATISTICAL CONSIDERATIONS

### STATISTICAL CONSIDERATIONS

This is a phase II study of lenalidomide as a maintenance therapy in patients with high risk AML and in first or second remission. The primary objective is to assess whether the maintenance therapy can improve relapse-free survival (RFS), which is defined as the time interval from date of treatment start until the date of death or disease relapse. Patients who are alive and relapse-free at the last follow-up date will be censored at that time.

The study will be continuously monitored for the primary endpoint, RFS, using the method of Thall, Wooten, and Tannir (2005). Our goal is to improve the median RFS from 8 months (based on historical treatment) to 10.5 months using lenalidomide maintenance therapy. It is assumed that the RFS time is exponentially distributed with a median of  $\lambda_E$  among patients who receive lenalidomide as a maintenance therapy, and a median of  $\lambda_H$  is assumed for the historical treatment. Further, we assume that  $\lambda_H$  follows an inverse gamma distribution, i.e.,  $\lambda_H \sim \text{IG}(3.6, 20.8)$ , which has a mean of 8 months and variance of 40. To reflect the little prior knowledge of  $\lambda_E$  we assume an inverse gamma prior distribution with the same mean of 8 months and a much larger variance of 500, i.e.,  $\lambda_E \sim \text{IG}(2.128, 9.024)$ . The trial will be stopped early if  $\text{Pr}(\lambda_E > \lambda_H + \delta | \text{data}) < pL$ , where  $\delta = 2.5$  months and  $pL=0.05$  and this futility monitoring rule will be first applied when 10 patients have been enrolled. A maximum of 50 patients will be enrolled into this study at an expected accrual rate of 1 patient per month. From historical experience, 25% of patients in this cohort may become eligible for stem cell transplant and may come off study. For purposes of this analysis, these patients will be censored at the time of receiving transplant. Patients will be followed up for an additional 12 months after all patients have been enrolled. The trial will be conducted using the Clinical Trial Conduct (CTC) website maintained by the Department of Biostatistics at MDACC.

The operating characteristics of the design, based on an overall assumed accrual rate of 2 patients per month with 5000 simulated trials per scenario, are given in the following table. One-Arm Time-to-Event Simulator (version3.0.1) was used for the design and simulation.

Scenario	True Median (months)	Pr(Stopped Early)	Mean No. patients	Average Trial Duration (months)
1	4	0.968	18.9	21.5
2	6	0.410	37.7	30.6
3	8	0.102	46.4	34.8
4	10.5	0.030	48.9	36.0

5	12	0.017	49.3	36.2
---	----	-------	------	------

For the primary analysis of the efficacy endpoint, we will compute the Bayesian posterior probability of  $\text{Pr}(\lambda_E > \lambda_H + \delta | \text{data})$ . As a secondary analysis, we will perform a competing risk analysis treating stem cell transplant as a competing event for RFS.

In addition, we will continuously monitor treatment-related toxicities using the Bayesian approach of Thall, Simon, Estey (1995). Specifically, the trial will be stopped if  $\text{Prob}(\pi T > 0.30 | \text{data}) > 0.92$ , where  $\pi T$  is the toxicity rate and we assume a beta (0.6, 1.4) prior for  $\pi T$ . That is, if at any given time, there is more than 92% probability that the toxicity rate of the maintenance therapy with lenalidomide is greater than 30%, the trial will be stopped. For the purpose of toxicity monitoring, toxicities are defined as any treatment-related clinically significant grade 3 or 4 non-hematologic AEs occurred any time during the trial, which are also outlined in Table 2. We will apply this stopping rule starting from the 10th patient and in cohort size of 10. The stopping boundaries corresponding to this toxicity monitoring rule are described in the following table:

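### The efficacy operating characteristics are simulated at 2 patients per month while the plan expects 1, so the average trial durations are up to about 25 months too short for the trial as planned

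*Combined protocol and SAP*

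**What the plan says.** All the relevant text is in Section 8.0 (Statistical Considerations) of the combined protocol and SAP.

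- Planned accrual: "A maximum of 50 patients will be enrolled into this study at an expected accrual rate of 1 patient per month".
- Follow-up: "Patients will be followed up for an additional 12 months after all patients have been enrolled".
- Basis of the efficacy table, in the very next paragraph: "based on an overall assumed accrual rate of 2 patients per month with 5000 simulated trials per scenario".

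The table then gives average trial durations of 21.5, 30.6, 34.8, 36.0 and 36.2 months for true median RFS of 4, 6, 8, 10.5 and 12 months. The 2-per-month rate is not described as a sensitivity case and is not explained. The section also expects that 25% of patients may go to transplant and be censored then, but does not say whether the simulation included this.

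**The concern.** Two adjacent paragraphs use accrual rates that differ by a factor of two. The table between them and the toxicity rule is the only account of how the RFS monitoring rule behaves, and its last column is the only trial duration stated. If accrual is 1 per month as planned, the table describes a faster trial than the one being run. Anyone planning drug supply, staffing, follow-up or oversight from it would expect a result in about three years, when the plan's own accrual implies about five.

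Accrual could also matter to the rule itself. Under continuous monitoring, slower accrual means more follow-up per enrolled patient at each look. The stopping probabilities and mean sample sizes therefore had to be checked as well.

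**Working it through.** **Inputs, all from Section 8.0**

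- RFS is exponential, with a target stated as: "Our goal is to improve the median RFS from 8 months (based on historical treatment) to 10.5 months".
- Historical median: IG(3.6, 20.8). Mean 20.8/2.6 = 8 and variance 8²/1.6 = 40, which agrees with the text.
- Experimental median: IG(2.128, 9.024). Mean 9.024/1.128 = 8 and variance 8²/0.128 = 500, which also agrees.
- Stop if Pr(λ_E > λ_H + 2.5 | data) < 0.05. On timing, "this futility monitoring rule will be first applied when 10 patients have been enrolled".
- Maximum 50 patients; 12 months of follow-up after the last enrolment.

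**Method.** With d events and total follow-up T, the posterior is λ_E ~ IG(2.128 + d, 9.024 + ln 2 × T), and λ_H keeps its prior. I simulated 5,000 trials per scenario with Poisson arrivals and checked the rule at each arrival from 10 patients. Duration is accrual time plus 12 months in every trial, including those stopped early.

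The last convention is inferred, not stated. It is what the table implies. In scenario 1, 18.9/2 + 12 = 21.45 against 21.5 stated, whereas with no follow-up after a stop the simulated figure would be 21.6 − 12 × 0.972 = 9.9 months.

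**Step 1: reproduce the stated table at 2 per month**

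| True median | Pr(stop): stated / rerun | Mean N: stated / rerun | Duration: stated / rerun |
|---|---|---|---|
| 4 | 0.968 / 0.972 | 18.9 / 18.3 | 21.5 / 21.6 |
| 6 | 0.410 / 0.424 | 37.7 / 37.2 | 30.6 / 30.8 |
| 8 | 0.102 / 0.119 | 46.4 / 45.9 | 34.8 / 35.0 |
| 10.5 | 0.030 / 0.033 | 48.9 / 48.8 | 36.0 / 36.4 |
| 12 | 0.017 / 0.019 | 49.3 / 49.3 | 36.2 / 36.6 |

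Every duration is within 0.4 month and every probability within 0.02. The table was run at 2 per month.

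**Step 2: the same rule at 1 per month**

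| True median | Pr(stop) | Mean N | Duration | Stated duration | Shortfall |
|---|---|---|---|---|---|
| 4 | 0.984 | 16.1 | 29.0 | 21.5 | 7.5 |
| 6 | 0.428 | 36.5 | 49.0 | 30.6 | 18.4 |
| 8 | 0.106 | 46.2 | 58.3 | 34.8 | 23.5 |
| 10.5 | 0.025 | 49.1 | 61.1 | 36.0 | 25.1 |
| 12 | 0.013 | 49.5 | 61.5 | 36.2 | 25.3 |

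Against the stated table, the largest change in stopping probability is 0.428 − 0.410 = 0.018. The largest change in mean N is 18.9 − 16.1 = 2.8 patients, at a median of 4.

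**Step 3: check without simulation.** A trial that enrols all 50 patients lasts 50/2 + 12 = 37 months at 2 per month and 50/1 + 12 = 62 months at 1 per month, a difference of 25 months. Using the table's own mean N for the last scenario, 49.3/1 + 12 = 61.3 against 36.2, a difference of 25.1.

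**Step 4: sensitivity**

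- Evenly spaced arrivals: the largest shortfall is 24.3 months.
- No follow-up after an early stop: at a median of 4, the 1-per-month duration falls to 29.0 − 12 × 0.984 = 17.2 months, below the stated 21.5. At a median of 12 it is 61.5 − 12 × 0.013 = 61.3, so the largest shortfall stays at about 25 months.
- Transplant censoring at 1 per month: the documents give no timing, so I assumed an exponential transplant time that censors 25% before an RFS event. Pr(stop) is 0.946 / 0.408 / 0.095 / 0.027 / 0.012, mean N 18.3 / 37.3 / 46.6 / 49.0 / 49.5 and duration 31.3 / 49.8 / 58.8 / 61.2 / 61.4. If instead a random 25% have transplant uniformly over months 0 to 6, Pr(stop) is 0.965 / 0.417 / 0.117 / 0.031 / 0.018.

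**The case against.** The table is openly labelled with its accrual rate and is correct for that rate, so this is an inconsistent input and not a miscalculation. Nothing in the documents shows which rate is right. If 2 per month is the true expectation, the durations stand and one figure in the accrual sentence changes. The columns that justify the stopping rule barely move, with or without transplant censoring. No sample size, boundary or calendar date is derived from the duration column, and a reader can work out 62 months from the paragraph just above the table.

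Most of this stands. The rule's performance is not in doubt, and the missing statement on censoring makes little difference to the figures. The objection does not remove the inconsistency. The expected rate is 1 per month, the only operating characteristics are for another rate, and neither is explained. A reader should not have to recompute the trial's duration to find that the table does not describe the planned trial.

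**Conclusion.** Wrong as written. Under the plan's expected accrual of 1 per month, the stated average durations are too short by about 7 months at a true median of 4, 18 months at 6, 23 to 24 months at 8, and 25 months at 10.5 and 12. At the target median, 36.0 months becomes about 61.

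This rests on 1 per month being the intended rate. The figures at short medians also depend on the inferred 12 months of follow-up after an early stop; the 25-month figure does not. The effect is confined to duration: stopping probabilities and mean sample size are close to those stated, and the design does not need to change. The correction should be made because the stated duration is materially misleading and cheap to put right.

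**What to change.** State one accrual rate throughout Section 8.0.

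- If 1 per month is intended, rerun the simulator at that rate with 25% of patients censored at transplant. State the assumed timing of transplant and whether follow-up continues after an early stop, and replace the table. The stated duration becomes about 61 to 62 months for a trial that is not stopped.
- If 2 per month is intended, correct the accrual sentence, keep the duration column, and say whether transplant censoring was simulated.

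The cost is one simulator run and a replaced table, or one corrected sentence. Sample size, priors, cut-off and first look stay as they are.
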